11.0 Evaluation Criteria

11.1 Measurement of Effect

Tumor response will be assessed, using contrast and non-contrast brain magnetic resonance imaging (MRI) with assessment based on the RANO criteria, until progression of disease (up to 5 years).

11.2 Definitions

Response and progression will be evaluated in this study using the international criteria proposed by the Response Assessment in Neuro-Oncology (RANO) Working Group [70]. Note: Lesions are either measurable or non-measurable using the criteria provided below. The term “evaluable” in reference to measurability will not be used because it does not provide additional meaning or accuracy.

11.21 Measurable Disease

Measurable disease is defined as bi-dimensionally contrast-enhancing lesions with clearly-defined margins by MRI, with two perpendicular diameters of at least 10 mm, visible on 2 or more axial slices which are preferably at most 5 mm apart with 0 mm skip. In the event the MRI is performed with thicker slices, the size of a measurable lesion at baseline should be two times the slice thickness. In the event there are inter-slice gaps, this also needs to be considered in determining the size of measurable lesions at baseline.

Measurement of tumor around a cyst or surgical cavity is problematic. In general, such lesions should be considered non-measurable unless there is a nodular component measuring at least 10 mm in diameter. The cystic or surgical cavity should not be measured in determining response. All tumor measurements must be recorded in millimeters (or decimal fractions of centimeters).

11.22 Non-measurable Disease

This is defined as either uni-dimensionally measurable lesions, masses with margins not clearly defined, or lesions with maximal perpendicular diameters <10 mm.

11.23 Target Lesions

All measurable lesions up to a maximum of five lesions should be identified as target lesions and recorded and measured (sum of the products of the perpendicular diameters) at baseline. Target lesions should be selected on the basis of their size (lesions with the longest diameters) and their suitability for accurate repeated measurements by imaging techniques. Occasionally, the largest

lesions may not be suitable for reproducible measurements and the next largest lesions which can be measured reproducibly should be selected.

11.24 Non-target Lesions

For patients with recurrent disease who have multiple lesions of which only one or two are increasing in size, the enlarging lesions should be considered the target lesions for evaluation of response. The other lesions will be considered non-target lesions and should also be recorded. Rarely, unequivocal progression of a non-target lesion requiring discontinuation of therapy, or development of a new contrast-enhancing lesion may occur even in the setting of stable disease (SD) or partial response (PR) in the target lesions. These changes would qualify as progression. Non-target lesions also include measurable lesions that exceed the maximum number of 5. Measurements of these lesions are not required but the presence or absence of each should be noted throughout follow-up.

11.3 Guidelines for Evaluation of Measurable Disease

All measurements should be taken and recorded in metric notation using a ruler or calipers. Baseline evaluations should ideally be performed within 21 days before the beginning of treatment. These techniques should be performed with cuts of 4 mm or less in slice thickness contiguously. The MRIs will be evaluated both locally and centrally by a core lab.

11.4 Response Criteria

11.41 Evaluation of Target Lesions

11.411 Complete Response (CR): Requires all of the following:

- Complete disappearance of all enhancing measurable and non-measurable disease sustained for at least 4 weeks
- No new lesions
- Stable or improved non-enhancing (T2/FLAIR) lesions
- Patients must be off corticosteroids
- Stable or improved clinically

Patients with non-measurable disease cannot have a complete response. The best response possible is stable disease.

11.412 Partial Response (PR): Requires all of the following:

- $\geq 50\%$ decrease compared to baseline in the sum of products of perpendicular diameters of all measurable enhancing lesions sustained for at least 4 weeks
- No progression of non-measurable disease
- No new lesions
- Stable or improved non-enhancing (T2/FLAIR) lesions on same or lower dose of corticosteroids compared to baseline scan
- The corticosteroid dose at the time of the scan evaluation should be no greater than the dose at time of the baseline scan
- Stable or improved clinically

Patients with non-measurable disease cannot have a partial response. The best response possible is stable disease.

- 11.413 Stable Disease (SD): Requires all of the following:
- Does not qualify for complete response, partial response, or progression
 - Minimum 4 weeks duration
 - Stable non-enhancing (T2/FLAIR) lesions on same or lower dose of corticosteroids compared to baseline scan. In the event that the corticosteroid dose has been increased, the last scan considered to show stable disease will be the scan obtained when the corticosteroid dose was equivalent to the baseline dose
 - Stable clinically
- 11.414 Progression: Defined by any of the following:
- $\geq 25\%$ increase in the sum of products of perpendicular diameters of enhancing lesions compared to the smallest tumor measurement obtained either at baseline (if no decrease) or best response, on stable or increasing doses of corticosteroids
 - Significant increase in T2/FLAIR non-enhancing lesion on stable or increasing doses of corticosteroids compared to baseline scan or best response following initiation of therapy, not due to co-morbid events (e.g. radiation therapy, demyelination, ischemic injury, infection, seizures, post-operative changes, or other treatment effects)
 - Any new lesion
 - Clear clinical deterioration not attributable to other causes apart from the tumor (e.g. seizures, medication side effects, complications of therapy, cerebrovascular events, infection, etc.) or changes in corticosteroid dose. The definition of clinical deterioration is left to the discretion of the investigator but it is recommended that a decrease in 20% of KPS or from any baseline to 50% or less be considered, unless attributable to co-morbid events.
 - Failure to return for evaluation due to death or deteriorating condition
 - Clear progression of non-measurable disease
- 11.415 Pseudoprogession (PsP): All of the following must be true:
- Progression of contrast enhancing lesions and or T2/FLAIR is restricted to the initial radiation therapy volume.
 - There are no new enhancing lesions outside of the initial radiation therapy volume.
 - Patients are stable or improved clinically.
 - PsP may be diagnosed at any time during therapy (beyond the typical 12 week window defined by RANO).

11.416 Summary of the RANO Response Criteria Table

	CR	PR	SD	PD^{1,2}	Preliminary PD/PsP³
T1-Gd +	None	≥50% decrease	<50% decrease- <25% increase	≥25% increase*	Any increase is restricted to initial RT Volume
T2/FLAIR	Stable or decrease	Stable or decrease	Stable or decrease	Increase*	Any increase is restricted to initial RT Volume
New Lesion	None	None	None	Present*	None
Corticosteroids	None	Stable or decrease	Stable or decrease	NA	Stable or decrease
Clinical Status	Stable or improved	Stable or improved	Stable or improved	Worsened*	Stable or improved
Requirement for Response	All	All	All	Any*	All

CR = complete response; PR = partial response; SD = stable disease; PD = progressive disease, PsP = Pseudoprogression

NA - Increase in corticosteroids alone will not be taken into account in determining progression in the absence of persistent clinical deterioration

- RANO Progression occurs when any of the criteria with * are present.
- Confirmed PD requires all of the following. If not all criteria are met then Preliminary PD
 - More than 3 months post RT
 - Radiologic progression by central review by RANO criteria
 - Clinical progression as determined by treating Oncologist
 - Because of the difficulty determining pseudoprogression from progression, and bevacizumab can be used to treat either progression or radiation-related treatment changes, treatment with bevacizumab alone does not qualify as progression. Clinical progression is determined by treating oncologist or initiation of systemic salvage regimens other than bevacizumab.
 - Cannot be considered Pseudoprogression
- Patients with possible PsP should initially be given the Objective Status of Preliminary Progression.
 - If Progressive Disease is subsequently confirmed, the Objective Status is to be recorded for the current cycle as PD (confirmed) and the back-dated date of the progressive disease (from the cycle with the initial Preliminary PD) is to be used as the date of progressive disease which is documented via the Event Monitoring Form.
 - If progressive disease is not confirmed the Objective Status for the current cycle can be documented as SD, PR, or CR as appropriate using the baseline scan measurement as the baseline for comparison with the current measurements. The Objective Status for the cycle initially documented as Preliminary PD can be changed to PsP.

11.417 Confirmatory Measurement/Duration of Response

11.4171 Confirmation

To be assigned a status of PR or CR, changes in tumor measurements must be confirmed by repeat assessments that

should be performed 4 weeks after the criteria for response are first met.

11.4172 Duration of Overall Response

The duration of overall response is measured from the time measurement criteria are met for CR or PR (whichever is first recorded) until the first date that recurrent or progressive disease is objectively documented (taking as reference for progressive disease the smallest measurements recorded since the treatment started).

The duration of overall CR is measured from the time measurement criteria are first met for CR until the first date that recurrent disease is objectively documented.

11.4173 Duration of Stable Disease

Stable disease is measured from the start of the treatment until the criteria for progression are met, taking as reference the smallest measurements recorded since the treatment started.

12.0 Descriptive Factors

- 12.1 Corticosteroid therapy at study entry: Yes (specify dose) vs. no
- 12.2 Histologic type of primary tumor: Oligodendroglioma vs. oligoastrocytoma vs astrocytoma vs other, specify
- 12.3 Histologic grade of primary tumor: 3 vs. 4
- 12.4 ECOG PS (see Appendix I): 0 vs. 1 vs. 2 vs. 3
- 12.5 Neurologic deficit: Yes vs. no
- 12.6 History of seizures: Yes vs. no
- 12.7 Prior surgical resection or biopsy: Yes vs. no
- 12.8 Age ≤ 70 vs. > 70
- 12.9a MGMT: Methylated vs. Unmethylated vs. Not available
- 12.9b Family history of brain tumor: Yes vs. no
If yes, check all that apply:
 Father/Mother
 Brother/Sister
 Child
 Other (list: _____)

13.0 Follow-up Decision at Evaluation of Patient

- 13.1 A patient is deemed *ineligible* if after registration, it is determined that at the time of registration, the patient did not satisfy each and every eligibility criteria for study entry. The patient will go off study.
- If the patient received MR and PET for radiotherapy planning, all data up until the point of confirmation of ineligibility must be submitted.
 - If the patient never received pre-RT PET, on-study material must be submitted.
- 13.2 On-study material and the End of Active Treatment/Cancel Notification Form must be submitted for patients who *cancel* participation prior to the start of pre-RT PET. These

materials must be provided to the MCCC Operations office. All data up to the point of going off study must be submitted to the MCCC Operations Office. No additional follow-up will be necessary.

- 13.3 Those patients who will *not* receive ^{18}F -DOPA PET image-guided dose escalation radiation treatment *or* who will receive radiation treatment elsewhere (other than specifically listed in section 6.4) will move to Event Monitoring phase.
- 13.4 Patients remain on study and continue to receive ^{18}F -DOPA PET scans at each clinically indicated MR scan until all of the following are confirmed / complete (up to 5 years or patient refusal):
- Radiological progression by central review per RANO criteria
 - Clinical progression identified by the treating oncologist
 - Because of the difficulty determining pseudoprogression from progression, and bevacizumab can be used to treat either progression or radiation-related treatment changes, treatment with bevacizumab alone does not qualify as progression. Clinical progression is determined by treating oncologist or initiation of systemic salvage regimens other than bevacizumab.
 - It is more than 3 months since radiation treatments have been completed, to ensure the radiological evidence is tumor progression versus treatment response
 - Note: the ^{18}F -DOPA PET scan (study imaging) during the patient visit at the time the above three conditions are met is highly desired and the patient is to be encouraged to complete it even if it is scheduled after the patient has been informed they have progressive disease.
- 13.5 Patients who develop Confirmed PD (both clinical and radiologic progression) or withdraw from further ^{18}F -DOPA PET scans will go to the event-monitoring phase per Section 18.0.

14.0 Body Fluid Biospecimens - None.

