4.0 Test Schedule

Tests and procedures	Active Monitoring				
	Baseline				Until PD or patient refusal
	≤21 days prior to registration	Cycle 1 Pre-RT Scans	Cycle 1 RT	Cycle 2 Post RT Scans ⁵ ≤42 days after RT	At every clinically indicated follow-up MR scan (end of each new cycle)
Physical exam, wt, ECOG PS	X				
Neuro history and exam	X			X	X
MMSE ⁴		X ¹²		X	X
CT simulation for radiotherapy planning	X ^{8,9}				
Pregnancy test		X ^{1,R}		X ^{1,R}	X ^{1,R}
¹⁸ F-DOPA-PET ^R		X ⁸		X	X ³
MRI with contrast/ RANO Assessment		X ^{6,8}		X	X ³
Advanced MRI		X ^{7,8}		X	X ³
¹⁸ F-DOPA adverse event assessment		X ²		X ²	X ²
Adverse event assessment ¹¹ (See Section 10.3)	X		X ¹⁰	X	X
QOL assessment ⁴		X ¹²		X	X
Concurrent Steroids and Anticonvulsants		X ¹²		X	X
MGMT Methylation Status	X ¹³				

1. For women of childbearing potential only. Must be done ≤48 hours prior to injection of study drug. Note: For a positive pregnancy test prior to the pre-RT ¹⁸F-DOPA injection the patient will not undergo the ¹⁸F-DOPA PET scan and will instead be taken off study with no follow-up. For any post-RT ¹⁸F-DOPA injection, the patient will not undergo the ¹⁸F-DOPA PET scan and will instead move to event monitoring.
2. ¹⁸F-DOPA post-injection assessment: done approximately 15-20 minutes post injection of ¹⁸F-DOPA and if AE observed a second AE assessment is required ≤24 hours post injection.
3. All follow-up serial imaging after initial treatment until progression up to 5 years. Note a typical grade IV follow-up schedule will include follow-up scans every 2 months for the first year after

radiation therapy, every 3 months for the second year, every 4 months for the third year, every 6 months after that. The actual timing of the follow-up scans for an individual patient will be per the clinician's discretion, e.g. if the clinician suspects possible progression, they may schedule more frequent follow-up imaging. While it is extremely unlikely (as current time to progression is 6 to 9 months), if a grade IV patient did not progress for 5 years, they may have up to 16 follow-up visits.

4. Patient will complete a maximum of 6 post-baseline QOL/MMSE evaluations
 5. Post RT scans to occur 3 to 6 weeks after RT is complete, to coordinate with first follow-up appointment
 6. Pre-treatment measurement

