8.0 Dosage Modification Based on Adverse Events

If a patient develops an allergic reaction during injection of ^{18}F -DOPA, the patient is not to receive any additional tracer and will not undergo PET imaging and will go off study.

9.0 Ancillary Treatment/Supportive Care: None.

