16.3 Analysis Plan

The analysis for this trial will commence at the planned timepoints (see 16.2) and at the time the patients have become evaluable for the primary endpoint. Such decision will be made by the Statistician and Study chair, in accord with the Cancer Center Statistics (CCS) Standard Operating procedures, availability of data for secondary endpoints, and the level of data maturity. It is anticipated that the earliest date in which the results will be made available via a manuscript, abstract, or presentation format is when 45 patients have either had confirmed-progression or been followed for at least 6 months. Subgroup analysis will be included for this primary endpoint to assess known prognostic factors such as performance status at baseline and age. Additionally, while no expected difference is anticipated, subset analysis will also be conducted for the primary endpoint to assess if there was any difference in patients treated via photons vs. protons.

16.31 Primary Endpoint:

16.311 Definition: The primary endpoint of this trial is the proportion of Grade-IV MGMT un-methylated patients that experience confirmed-progression-free survival at 6 months from the time of craniotomy. All Grade IV MGMT un-methylated patients meeting eligibility criteria who have signed a consent form and who have begun RT treatment will be evaluable for the endpoint. All eligible patients will be followed until death or a maximum of 5 years. Time to confirmed-progression is defined as the time from initial surgery to the earliest date documenting confirmed-progression. If a patient dies without documentation of disease progression, the patient will be considered to have had tumor

progression at the time of death. If a patient is declared to be a major treatment violation, the patient will be censored on the date the treatment violation was declared to have occurred. In the case of a patient starting treatment and then never returning for any evaluation, the patient will be censored for progression on the last day of therapy.

- 16.312 Estimation: The proportion of CPFS6 successes and associated 95% confidence intervals will be estimated using Kaplan-Meier analysis methods.
- 16.313 Over Accrual: If more than the target number of patients are accrued, the additional patients will not be used to evaluate the stopping rule or used in any decision making processes; however, they will be included in final point estimates and confidence limits.

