Determine acute and late effect toxicity after radiotherapy treatment targeting dose escalated volumes defined to include high ^{18}F -DOPA PET uptake. The rate of acute and late treatment-related toxicities for newly diagnosed high-grade glioma patients treated with ^{18}F -DOPA PET image-guided dose escalation will be determined, with acute RT toxicities graded using Common Terminology Criteria for Adverse Events (CTCAE) v4.0 (available at <http://ctep.cancer.gov>), and late toxicities reported using the RTOG/EORTC late toxicity criteria [71]. Patients will be considered evaluable for adverse events if they receive ^{18}F -DOPA PET or ^{18}F -DOPA PET image-guided dose escalation RT.

16.326 Compare confirmed-progression free survival at 12 months for Grade IV MGMT-methylated patients after radiation therapy targeting volumes designed with both ^{18}F -DOPA PET and conventional MR image information with historical controls from Mayo Clinic Rochester patients, including those on clinical trials.

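### Sections 13.1 and 8.0 take patients off study with no exception for those already given dose-escalated RT, which conflicts with the follow-up in 16.311 and leaves gaps in the toxicity counts of 16.325 and 16.42.

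*Combined protocol and SAP*

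**What the plan says.** **Rules that take patients off study.** Section 13.1 applies when it is found after registration that "the patient did not satisfy each and every eligibility criteria for study entry. The patient will go off study". If planning MR and PET were done, "all data up until the point of confirmation of ineligibility must be submitted"; nothing is requested after that date. Section 8.0 says that after an allergic reaction during injection "the patient is not to receive any additional tracer and will not undergo PET imaging and will go off study". It does not separate the planning scan from the follow-up scans, which 7.21 continues until progression for up to 5 years.

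**What the analysis expects.** Section 16.311 limits the primary endpoint to patients who meet the eligibility criteria and have begun RT, and adds: "All eligible patients will be followed until death or a maximum of 5 years". Section 16.325 says: "Patients will be considered evaluable for adverse events if they receive" the tracer PET or the PET-guided dose-escalated RT, with no eligibility condition. The RT toxicity rule in 16.42 acts when more than 10% of enrolled patients have a listed event.

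**How other patients are handled.** Section 13.5 sends those who withdraw from further tracer "PET scans will go to the event-monitoring phase per Section 18.0". Note 1 of Section 4.0 separates two cases. A positive pregnancy test before the planning injection means that the patient does not have the "PET scan and will instead be taken off study with no follow-up"; before a post-RT injection, the patient moves to event monitoring.

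**The concern.** The boost is the experimental exposure, so late CNS toxicity in everyone who received it is what the safety analysis most needs. Two rules written around eligibility and the tracer also decide how long that exposure is observed.

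- **Toxicity.** An irradiated patient removed under 13.1 or 8.0 stays in the 16.325 population and in the 16.42 denominator, while later events may not reach the numerator. That biases the observed rate downwards.
- **Primary endpoint.** An eligible un-methylated patient who reacts at a post-RT scan within 6 months of craniotomy stays in the CPFS6 set. Section 16.311 has censoring rules for major violations and for patients who never return, but none for removal under 8.0. The decision rule in 16.21 needs a count of successes.

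**Working it through.** **1. The disposition rules side by side**

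| Situation | Section | Destination |
|---|---|---|
| Will not receive dose-escalated RT, or has RT elsewhere | 13.3 | Event monitoring |
| Withdraws from further PET | 13.5 | Event monitoring |
| Positive pregnancy test, post-RT injection | 4.0 note 1; 7.22 | Event monitoring |
| Positive pregnancy test, planning injection | 4.0 note 1 | Off study, follow-up expressly ended |
| Cancels before planning PET | 13.2 | Off study, further follow-up expressly not needed |
| Tracer allergy, any injection | 8.0 | Off study |
| Found ineligible, any time | 13.1 | Off study, data to confirmation only |

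A patient who never has the boost is followed under 13.3. One who had it and is later found ineligible, or reacts to the tracer, is not, if the text is applied as written.

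**2. Is there another channel for late toxicity?** Section 10.41 exempts CNS necrosis up to Grade 3 from expedited reporting. The table in 10.6 collects it only in Active Monitoring. Section 10.62 mentions late events after Active Monitoring but defers to a forms packet and sets no schedule for off-study patients. The event-monitoring table in 18.13 has no RT toxicity form. Yet irreversible CNS toxicity of Grade 3 or 4 is a trigger in 16.42.

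**3. How many tracer reactions?** Section 1.7 reports no tracer-related adverse event in 82 patients and 174 injections. One-sided 95% upper bounds:
- per patient: 1 − 0.05^(1/82) = 3.6%
- per injection: 1 − 0.05^(1/174) = 1.7%

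At the per-patient bound, 0.0359 × 93 = 3.3 of all patients and 0.0359 × 45 = 1.6 of the primary set. These figures include planning-scan reactions, before any boost. They rest on 174/82 = 2.1 injections per patient; some patients here will have more, so they are a guide.

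**4. Effect on the primary decision.** With X1 ~ Bin(25, p) and X2 ~ Bin(20, p), P(positive) = Σ over x = 16 to 25 of P(X1 = x) × P(X2 ≥ 30 − x). This gives 0.195 at p = 0.60 and 0.804 at p = 0.725. Stage 1 stopping is 0.575 and 0.122. All agree with 16.24.

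Now let k second-stage patients have unknown 6-month status and not be replaced, so X2 ~ Bin(20 − k, p). The threshold is 30 − x if they count as failures and 30 − k − x if they count as successes. Here k is an assumption; step 3 suggests 0 to 2.

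| k | Failures: type I error / power | Successes: type I error / power |
|---|---|---|
| 0 | 0.195 / 0.804 | 0.195 / 0.804 |
| 1 | 0.155 / 0.762 | 0.222 / 0.821 |
| 2 | 0.117 / 0.704 | 0.249 / 0.834 |

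**5. Effect on the RT toxicity rule.** With 93 enrolled, more than 10% means at least 10 events. P(trigger) at a single look at full enrolment is P(Bin(93 − m, q) ≥ 10), where m patients have unseen events. Both m = 5 and the true rate q are assumptions.

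| q | m = 0 | m = 5 |
|---|---|---|
| 10% | 0.454 | 0.385 |
| 15% | 0.907 | 0.868 |
| 20% | 0.994 | 0.989 |

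**The case against.** The case against is that this is mainly loose wording about very few patients.

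- **Follow-up is not expressly ended.** Neither 13.1 nor 8.0 says so, whereas 13.2 and note 1 of Section 4.0 do. This stands: the end of routine collection is an inference, though the natural one for a patient who is off study.
- **Other reporting duties continue.** Related serious events (10.4, footnote 1), disabling events (10.51), related deaths (10.52) and secondary malignancies (10.53) stay reportable. A reader might infer that these patients' toxicity and outcome are lost altogether; the documents do not support that. Data up to confirmation of ineligibility are also kept. What remains exposed is routine grading, including CNS necrosis up to Grade 3.
- **Section 16.325 defines who is evaluable, not for how long.** True. For ineligible patients the problem is therefore incomplete capture within a defined population, not a direct contradiction.
- **Event monitoring collects no RT toxicity either.** Also true, and routine grading under 10.6 stops at progression. Sending these patients to event monitoring would restore progression and survival data but not toxicity.
- **Late-found ineligibility should be uncommon,** since 6.3 verifies eligibility before registration. That is plausible, but the documents give no rate. The 5 extra patients in 16.22 also cover cancellation, violation and other reasons.

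**Conclusion.** The point holds in two parts of different strength.

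1. For an eligible patient who reacts at a post-RT scan, 8.0 contradicts 16.311 and is inconsistent with 13.5 and note 1 of Section 4.0. If it happens before 6 months, CPFS6 has no outcome for that patient.
2. For a patient found ineligible after RT has begun, 13.1 appears to stop routine toxicity collection, while 16.325 and 16.42 still count the patient.

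A reader might go further and infer that 13.1 also removes patients on whom the primary endpoint relies. It does not: 16.11 and 16.311 both require eligibility, so leaving these patients out of CPFS6 is consistent. Only the sentence in 16.21 that defines endpoint-evaluable by treatment alone is looser. Nor should the 10% allergy threshold in 16.42 be read as a forecast. Ten per cent of 93 is 9.3, so 9 reactions would not trip it, but that is the rule's ceiling; none was seen in 82 patients.

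The numbers affected are probably small. One unresolved second-stage patient moves power from 0.804 to between 0.762 and 0.821. Five patients with unseen events lower the chance of triggering the toxicity rule from 0.907 to 0.868 at an assumed 15% rate. The safety gap is the stronger reason to act, and correction is cheap.

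**What to change.** Reconcile 8.0, 13.1, 13.5, 16.311 and 16.325 with one data-collection statement:

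- Any patient who has begun dose-escalated RT, and then goes off study PET or is found ineligible, continues to contribute RT toxicity data on the 10.6 schedule at standard MRI visits, with progression and survival data, up to 5 years while consent stands.
- Ineligible patients remain outside CPFS6 but stay in the 16.325 and 16.42 toxicity counts.

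The statement should set no rule on tracer, scans or treatment. The design is unchanged: 45 evaluable patients, type I error 0.195 and power 0.804. The cost is a short amendment and a little extra data collection on a few patients.
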